## 1.0 Objectives

Increased duration of untreated psychosis (DUP), defined as the time from manifestation of the first psychotic symptom(s) to initiation of evidence-based treatment, is associated with poorer clinical and functional outcomes (Fusar-Poli et al., 2009). Factors associated with longer DUP include perceived barriers to care among those experiencing psychotic-like symptoms and feelings of not being listened to or not being offered the opportunity to make decisions regarding treatment (referred to as shared-decision making). The primary objective of our proposed study is to investigate the association between DUP and perceptions regarding barriers to care and shared-decision making among college students. The secondary objective is to conduct a process evaluation of the inclusion of a screening tool (the Prodromal Questionnaire Brief- PQ-B developed by Loewy et al., 2011) during triage at University of New Mexico Student Health and Counseling Center (SHAC). SHAC implemented the PQ-B August 1st, 2020 to improve quality of clinical services by identifying students at risk of first episode psychosis (FEP) and referring those identified at high risk to coordinated specialty care programs (i.e., Early and CONNECT) in the Department of Psychiatry and Behavioral Sciences, University of New Mexico. The Early Program is a coordinated specialty care program for the young adults experiencing first episode psychosis (FEP) while the CONNECT program provides stepped care to young individuals at clinical high risk (CHR) of developing psychosis.

The specific aims are to:

1. Measure DUP among University of New Mexico (UNM) college students enrolled in the Early or CONNECT Programs in the Department of Psychiatry and Behavioral Sciences and identify other factors that may contribute to longer DUP, such as perceptions relating to barriers to mental health care and shared decision-making. We hypothesize that there will be: (1) a positive association between DUP and the number of perceived barriers to care, and (2) a negative association between DUP and feelings of shared-decision making.

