## 2.0 Background

2.1 General Background. Clinical and general population studies on FEP have generated enough evidence to have confidence in three issues. First, the DUP is a strong predictor of outcome, such that current clinical recommendations are <3-6 months

PROTOCOL TITLE: Duration of Untreated Psychosis and Perceived Barriers to Mental Health Care Among College Students

(Compton et al., 2008). Second, in the U.S., individuals are still presenting with DUP on average of two years (Marshall et al., 2005). Third, the reasons for treatment delay are multiple and complex (Apelodoorn et al., 2014). Various classifications have been developed to categorize the factors that contribute to an extended DUP. Compton and Broussard (2011) for example, identified six categories, including: (i) demographic, (ii) premorbid and onset-related, (iii) illness-related, (iv) family-level, (v) societal, and (vi) health system and service level factors.

With the first symptoms of psychosis being most likely to surface around ages 15 to 24, college age young adults are at increased risk of FEP and CHR of psychosis (Kessler et al., 2007; Simon et al., 2017). Studies on the course of schizophrenia indicate that the initial onset of the disorder shows a steep increase during adolescence and young adulthood and then begins to decrease around the age of 25 (Hafner et al., 1993; Sham et al., 1994). Simon et al., (2017) reported a FEP incidence rate of 86 per 100,000 among ages 15-29 compared to 46 per 100,000 among 30-59 across a variety of care settings. There are other environmental risk factors unique to college students that may increase risk of psychosis and contribute to increased DUP. First, attending college can be a stressful time for many students, learning to live independently and handle college level work load. Second, there are higher rates of illicit and prescription drug use among college students. Third, lack of identification of mental health symptoms and/or treatment have surfaced as system-level challenges on college campuses. This contributes to the persistence of mental health problems among students, partly due to the under-resourcing of college mental health services in relationship to needs. Lastly, many college students are in the process of transitioning between adolescence to adulthood and may be less likely to recognize when to seek help or to feel comfortable with accessing services independent of family support.

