**2.3. Contribution to the Literature.** Upon successful completion of the proposed research, we expect our contribution to the literature to be preliminary data on DUP among college students and perceptions regarding barriers to receiving mental health care and shared-decision making.

The quality improvement data will also contribute to the literature on screening for first episode psychosis among a college population.

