**Demographic Data:** Basic demographic data will be collected on each participant, including city of birth, phone number and email (for future contact), current education year, date of birth, sex, gender, race and ethnicity. City of birth and full date of birth are required to obtain a Global Unique Identifier (GUID) in the NIMH Data Archive. A GUID is a subject ID allowing researchers to share data specific to a study participant without exposing personally identifiable information. A copy of the demographic form has been attached.

**Structured Clinical Interview for DSM-5 (SCID-5)** (First et al., 2015). The SCID-5 Research Version will be used to confirm clinical diagnoses for all participants enrolled in the research study. Only the sub-units for psychosis, mood disorders, substance abuse and trauma-related disorders will be completed. The SCID-5 will be administered by the research coordinator who has been trained in its use and achieved sufficient reliability for research purposes.

**Duration of Untreated Psychosis (DUP)** will be collected using the Circumstances of Onset and Relapse Schedule (CORS) (Norman and Malla, 2002). The CORS includes

**PROTOCOL TITLE:** Duration of Untreated Psychosis and Perceived Barriers to Mental Health Care Among College Students

the Topography of Psychotic Episode (TOPE), which together traces the process of seeking treatment by identifying step-by-step contacts with medical and mental health services in the pathway toward contact with early psychosis services. The CORS protocol includes specific questions and follow-up prompts to help determine the onset of prodromal and psychotic symptoms and pathways to care (Attachment 2). The CORS has well established psychometric properties and takes approximately an hour to complete. It will be completed by the Research Coordinator or PI through semi-structured interviews. While participants identified as at CHR for psychosis, by definition, would not yet have had a psychotic episode, we will similarly record onset of attenuated psychosis symptoms in order to better understand barriers and pathways to care for this group.

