## **11.0 Data and Specimen Management**

**11.1** *Describe the data analysis plan, including any statistical procedures.* The goals of this study are to (1) measure DUP and perceptions regarding barriers to care and shared-decision making, and (2) conduct a process evaluation of the implementation of the PQ-B (a screening tool to identify risk of psychosis) at SHAC. Descriptive statistics (e.g., means, standard deviations, medians, quartiles) and summary statistics (for the process evaluation) statistics (will be calculated to summarize the characteristics of the student population, to summarize instrument scores, and to summarize process data regarding the PQ-B at an aggregate level . DUP among those with FEP and duration of

PROTOCOL TITLE: Duration of Untreated Psychosis and Perceived Barriers to Mental Health Care Among College Students

attenuated symptoms among those with CHR will be reported in days as a mean and 95% exact Poisson CIs. We will report the mean BSPHS summed scores and 95% CIs.

*11.2 Provide a power analysis, if necessary.* Not Applicable

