## **22.0 Number of Subjects**

We expect to enroll approximately 40 students into the study over the study period.

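### Section 11.1 puts an exact Poisson confidence interval on mean durations, which are not counts, so the interval takes nothing from the observed spread between people

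*Combined protocol and SAP*

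**What the plan says.** Section 1.0 describes DUP as a length of time: "defined as the time from manifestation of the first psychotic symptom(s) to initiation of evidence-based treatment". Section 9.2 says high-risk participants, "by definition, would not yet have had a psychotic episode, we will similarly record onset of attenuated psychosis symptoms". For these participants it names an onset but no end date. Data are collected from each participant once (Section 9.1).

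The interval sentence in Section 11.1 is split by a page header. It opens with "DUP among those with FEP and duration of" and continues with "attenuated symptoms among those with CHR will be reported in days as a mean and 95% exact Poisson CIs". The next sentence treats the barriers score differently: "We will report the mean BSPHS summed scores and 95% CIs". The Poisson wording therefore applies to the two durations only. Section 11.1 also lists SDs, medians and quartiles among its general descriptive statistics, without linking them to this interval. Section 11.2 gives no power analysis, and Section 22.0 states: "We expect to enroll approximately 40 students into the study over the study period".

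**The concern.** An exact Poisson interval is built for a number of events, and its variance is fixed by the count itself. Here each person supplies one duration. Whole days are units of measurement and not independent events, so a person with a DUP of 730 days has not had 730 events. The plan does not say what is to be counted, and the candidate choices give very different widths. None of them uses the variation actually seen between participants.

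Section 2.3 names "preliminary data on DUP among college students" as an expected contribution of the study. With about 40 students in total, divided between two groups, the interval is what tells a reader how imprecise the mean is.

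**Working it through.** The plan states no interval width or SD, so there is no figure of its own to reproduce. The check compares the possible readings with an interval that uses the SD.

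**Inputs.**
- Total sample about 40 (Section 22.0). The split between groups is not given, so n = 10, 20 and 30 per group were tried.
- Mean of 730 days, from the general US statement in Section 2.1: "individuals are still presenting with DUP on average of two years". This is not a college figure. A mean of 90 days was also tried, from the lower end of the recommended range in Section 2.1.
- SD not given. Assumed coefficients of variation (CV = SD/mean) were 0.5, 1 and 1.5.

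**Formulas.** For a count k, the exact limits are L = χ²(0.025; 2k)/2 and U = χ²(0.975; 2k+2)/2.
- (a) Total days as the count: k = n × mean, limits L/n and U/n. This is the most natural reading of a mean in days.
- (b) The mean as a single count: k = mean.
- (c) n treatment starts over total person-days, inverted: k = n, limits total days/U to total days/L. This assumes exponential durations.
- Comparator: t interval, half-width t(0.975; n−1) × SD/√n.

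**Same data, n = 20, mean 730 (total 14,600 days):**

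| Reading | Limits (days) | Width (days) | Coverage at CV 1 |
|---|---|---|---|
| (a) | 718.2 to 741.9 | 24 | about 6% |
| (b) | 678.0 to 784.9 | 107 | 25–26% |
| (c) | 472.7 to 1195.1 | 722 | 96–97% |

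At CV 1 the SD is 730, and the t half-width is 2.093 × 730/√20 = 341.7 days. The half-width of (a) is 11.9 days, a ratio of about 29.

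**Without assuming a CV.** Reading (a) matches the t width only if SD = half-width × √n / t. At mean 730 that is 23.5, 25.4 and 25.9 days for n = 10, 20 and 30. At mean 90 it is 8.3, 8.9 and 9.1 days.

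**Spread is ignored.** Forty people all at 730 days, and 20 at 30 days plus 20 at 1430 days (SD 709), give the same interval under (a): 721.7 to 738.4. The t half-widths are 0 and 227 days.

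**The unit changes the answer.** Under (a) with n = 40 and mean 730, analysing in days, weeks, months or years gives half-widths of 8.4, 22.2, 46.6 or 164.9 days.

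**Simulated coverage of a nominal 95% interval** (gamma and lognormal durations rounded to whole days, 40,000 samples per setting, n = 10, 20, 30, means 90 and 730, CV 0.5 to 1.5):
- (a): 4–12% at mean 730; 11–32% at mean 90.
- (b): 12–98% across all settings.
- (c): about 100% at CV 0.5, 96–97% at CV 1, 83–89% at CV 1.5.
- t interval: 82–94%.

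**The case against.** The strongest reply is that the very low coverage belongs mainly to reading (a), and the plan does not say that (a) is meant. Under (c), an exact Poisson calculation does give a valid interval for a mean if durations are exponential, and Section 1.0 supplies an end event for DUP, the start of treatment. At CV 1, (c) covers at least as well as the t interval; at CV 1.5 the two are similar. Reading (b) can also come close to 95% when the mean is short and the CV small.

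This limits any claim that the interval must be too narrow, but it does not rescue the sentence. Section 11.1 mentions no rate, and for high-risk participants no end event is named. The width of (c) is still fixed by n and the mean, so it is too wide at CV 0.5 and too narrow at CV 1.5.

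A second reply is that the SDs and quartiles listed in Section 11.1 would show the spread anyway. They would, but they would not correct the printed interval.

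Third, this is a descriptive result in a study that presents itself as preliminary. That is right, and it bounds the importance of the point.

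**Conclusion.** The concern holds. The stated method does not suit the quantity, the count is undefined, and no reading uses the observed SD. On identical illustrative data the width runs from 24 to 722 days according to an unstated choice. On the most natural reading the interval is far too narrow unless between-person SDs are implausibly small: about 23 to 26 days on a mean of 730, or 8 to 9 days on a mean of 90.

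The exact coverage figures rest on assumed CVs, group sizes, means and distribution shapes; the mismatch between method and quantity does not. The consequence is confined to the descriptive intervals under Aim 1. Neither association hypothesis, no decision rule and no sample size depends on them. It should be fixed, but it does not threaten the study.

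**What to change.** Delete the exact Poisson wording and replace the sentence in Section 11.1 with:

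> DUP (FEP) and duration of attenuated symptoms (CHR) will be reported separately, in days, as mean and SD with a 95% t interval for the mean based on the observed SD, and as median and IQR.

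Preferably add an order-statistic 95% interval for the median in any group with at least 6 participants. It is slightly conservative (97.9% at n = 10, 95.9% at n = 20, 95.7% at n = 30) and suits skewed durations. The end date of the CHR duration also needs stating, since Section 9.2 gives only an onset.

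The cost is one sentence and no new data. Intervals will usually be wider than under reading (a). The t interval is imperfect for skewed durations in small groups: besides the under-coverage shown above, its lower limit can fall below zero (at CV 1.5, in 15–35% of samples at n = 10 and about 2% at n = 20; at CV 1 and n = 10, 3–4%). A log-scale or bootstrap interval would be a reasonable alternative, provided it uses the observed spread and is named in advance.

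### Section 11.1 names only a mean for DUP and for duration of attenuated symptoms; if these durations are right-skewed, a few long cases can dominate that figure, and it does not show how many FEP students fall within 3-6 months

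*Combined protocol and SAP*

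**What the plan says.** Section 11.1 has one sentence specific to the two durations. DUP in FEP students and duration of attenuated symptoms in CHR students "will be reported in days as a mean", with 95% intervals by the exact Poisson method. It gives no median, quartiles, transformation or proportion below a threshold for either.

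The sentence before it offers a general list, "Descriptive statistics (e.g., means, standard deviations, medians, quartiles", to be applied to student characteristics, PQ-B process data and "to summarize instrument scores". DUP is not named there. It is, however, obtained with a named instrument: Section 9.2 says that it "will be collected using the Circumstances of Onset and Relapse Schedule (CORS".

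Section 2.1 gives the context. It states that "current clinical recommendations are <3-6 months" and that in the U.S. "individuals are still presenting with DUP on average of two years". Section 22.0 gives the size: "We expect to enroll approximately 40 students into the study over the study period". That total covers FEP and CHR together, and the split is not given.

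**The concern.** Measuring DUP is the first goal listed in Section 11.1, and Section 2.3 offers preliminary DUP data in college students as the expected contribution. The figure chosen to summarise DUP will therefore be the study's main descriptive result.

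DUP is a time from first symptoms to treatment. It cannot fall below zero, and the plan sets no upper limit. Such times often have a long right tail, and then two things follow. In a small group, one or two people can set the mean. And very different groups can share the same mean: one in which hardly anyone is treated within six months, and one in which most are. A reader who sees a mean well above 180 days could conclude that most students exceeded the cited recommendation when most had met it.

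**Working it through.** The documents state no precision or sample-size figure for DUP, so there is no planned number to reproduce. The check asks how much a mean alone leaves open.

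**Inputs from the documents.** Average DUP two years, taken as 730 days (Section 2.1). Recommendation below 3-6 months, taken as 90 and 180 days (Section 2.1). About 40 students in all (Section 22.0).

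**Assumptions, not in the documents.** Log-normal DUP; log-SD *s* from 0.5 to 2.0; 20 FEP students.

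**Step 1: same mean, different groups.** With the mean fixed at 730, μ = ln(730) − s²/2, the median is exp(μ), and the share below *d* days is Φ((ln *d* − μ)/s). For example, at s = 1.5, μ = 6.593 − 1.125 = 5.468. The median is exp(5.468) = 237, and the share under 180 days is Φ((5.193 − 5.468)/1.5) = Φ(−0.183) = 43%.

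| log-SD | Mean | Median | Under 90 days | Under 180 days |
|---|---|---|---|---|
| 0.5 | 730 | 644 | 0% | about 1% |
| 1.0 | 730 | 443 | 6% | 18% |
| 1.5 | 730 | 237 | 26% | 43% |
| 2.0 | 730 | 99 | 48% | 62% |

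**Step 2: weight of the longest case.** Simulated samples of 20; typical (median) values across samples.

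| log-SD | Share of all days held by the longest case | Fall in the mean if it is removed |
|---|---|---|
| 0.5 | 11% | 6% |
| 1.0 | 20% | 16% |
| 1.5 | 30% | 26% |
| 2.0 | 40% | 37% |

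**Step 3: sampling spread at n = 20.** Central 95% of simulated samples, in days, with the ratio of upper to lower limit.

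| log-SD | Sample mean | Ratio | Sample median | Ratio |
|---|---|---|---|---|
| 0.5 | 575 to 917 | 1.6 | 495 to 839 | 1.7 |
| 1.0 | 418 to 1,242 | 3.0 | 259 to 760 | 2.9 |
| 1.5 | 266 to 1,840 | 6.9 | 109 to 532 | 4.9 |
| 2.0 | 140 to 2,752 | 19.7 | 34 to 292 | 8.6 |

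The median is clearly steadier only at 1.5 and above.

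**Step 4: an example without the log-normal form.** Take 36 students at 120 days and 4 at 1,825 days. Total days are 36 × 120 + 4 × 1,825 = 4,320 + 7,300 = 11,620. The mean is 11,620/40 = 290.5 days and the median is 120. The mean lies above six months although 36/40 = 90% lie below it, and the four long cases hold 7,300/11,620 = 63% of the days. With 18 and 2 students the results are the same.

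**Step 5: the interval attached to the mean.** The exact Poisson limits treat total days as one count: χ²(0.025; 2T)/(2n) to χ²(0.975; 2T + 2)/(2n), where T is total days. At n = 20 and T = 14,600 this gives 718 to 742 days. In the same simulations it contained the true mean in about 11% of samples at log-SD 0.5 and about 1% at 2.0, against a nominal 95%. Keeping the mean therefore requires a different interval.

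**The case against.** **Medians and quartiles are already planned.** The general list includes them, DUP comes from an instrument, and nothing says that the mean is the only figure. A reader might infer that the plan ignores medians altogether, and the documents do not support that. What remains is that the list is introduced as examples, does not name DUP, and is followed by a sentence that specifies a mean for DUP. The analyst is left to choose, and no share within 3-6 months is planned under either reading.

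**A mean can be compared with the recommendation.** A reader might infer that a mean cannot be set against 3-6 months at all. Section 2.1 itself puts a two-year average beside that recommendation. The narrower statement stands: the mean does not give the number of students who meet it. The mean is also needed for comparison with the cited average, so it should be kept.

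**The recommendation is background, not an aim.** This is correct. No objective or endpoint classifies students against it, so the threshold counts are a useful addition and not the repair of a broken promise. It also concerns DUP, and no limit is cited for attenuated symptoms, so the counts belong to FEP only.

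**Skew is assumed.** This also stands. The documents give no SD, median or distribution. At log-SD 0.5 the mean and median are close (730 and 644) and the mean is slightly the steadier. The heavier tails sit uneasily with an age range of 15-30 (Section 3.2). The chance that a sample of 20 contains a DUP above 15 years (5,475 days) is 1 − Φ(2.093)^20 = 31% at log-SD 1.5 and 1 − Φ(2.007)^20 = 36% at 2.0. Steps 2 and 3 therefore overstate tail dominance at that end.

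**Conclusion.** The concern holds in a limited form. The only summary that Section 11.1 ties to either duration is a mean, and a mean alone leaves the main descriptive result open to misreading. A mean of 730 days is compatible with anything from about 1% to 62% of students under 180 days across the assumed log-SDs. The four-long-cases example shows that the difficulty does not depend on the log-normal form.

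The size is conditional. It rests on right skew, an assumed range of log-SDs and an assumed 20 FEP students, none of which the documents give. With mild skew the effect is small. The documents do not show that DUP will be skewed or that the planned mean will be wrong. This is a low-cost improvement to an underspecified headline figure. Within the same sentence the Poisson interval is the graver fault, and changing the location measure without replacing that interval would leave it in place.

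**What to change.** Rewrite the DUP sentence in Section 11.1 to provide the following.

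- For DUP (FEP) and duration of attenuated symptoms (CHR), separately: median and quartiles in days, with an order-statistic 95% CI for the median. With 20 students this runs from the 6th to the 15th ordered value, with exact coverage 1 − 2 × P(Bin(20, 0.5) ≤ 5) = 1 − 2 × 0.0207 = 95.9%.
- For FEP only: number and percentage with DUP under 90 and under 180 days, with exact binomial 95% CIs.
- The mean as a supplement for comparison with the cited two-year average, with an interval that reflects between-student variation (for example bootstrap or log-scale) in place of the exact Poisson CI. If the data prove strongly skewed, say that an interval for the mean is itself unreliable in a group this small: in the simulations at n = 20 an ordinary t interval covered 93%, 87%, 76% and 63% at log-SD 0.5, 1.0, 1.5 and 2.0.

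The cost is a few lines of text and slightly more reporting. No new data are needed, and if the durations prove nearly symmetric nothing is lost, because the mean is still reported.
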